Aim 1. To compare the impact of training PCMH clinician to deliver BBTI (BBTI) vs. the impact of BBTI training plus 12-months of access to an implementation strategy bundle (BBTI+IS). Sites will be measured across three study phases: BBTI (pre-implementation), BBTI+IS (implementation), and maintenance (post-implementation). During the implementation phase, sites will have internal and external support from insomnia and implementation experts to enhance their implementation efforts. We hypothesize that BBTI+IS will result in more Veterans obtaining insomnia-related care in PCMH (R [primary outcome]), better treatment outcomes (E), greater uptake of BBTI by clinicians (A), improved treatment fidelity (I), and result in sustained BBTI delivery without implementation support (M). RE-AIM outcomes will allow for the evaluation and refinement of specific implementation strategies to use in future efforts to improve access to evidence-based insomnia care.

Aim 2. To identify specific strategies that help promote the implementation of BBTI in PCMH. Using qualitative interviews, we will evaluate site PI and PCMH clinician perspectives on BBTI training, and the impact of implementation strategies and barriers that continue to impede progress. Using surveys, completed by site PIs, we will identify specific strategies that help, or hinder, the implementation of BBTI in PCMH. Strategies identified as helping to implement BBTI in PCMH will help further adapt strategies to enhance implementation.

This proposal is responsive to VA ORD priorities of expanding access to Veterans for high quality clinical trials (e.g., a stepped-wedge, hybrid trial) and increasing the real-world impact of VA research. It also targets HSR&D research, and ORD clinical, priority areas of access to care, mental health, primary care practice, and virtual care and telehealth, within the framework of implementation science, a prioritized cross-cutting method.

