## 5.1 Study Procedures

### 5.1 Study Design

Overview of Experimental Design and Timeline. This is a four-year, stepped-wedge, hybrid III implementation-effectiveness trial comparing two conditions: training PCMH clinicians to deliver BBTI (BBTI) vs. training clinicians to deliver BBTI augmented by access to, and support for, a bundle of expert-consensus implementation strategies (BBTI+IS). The goal of this trial is to determine if a bundle of implementation strategies can improve the uptake and sustainable delivery, and treatment outcomes, of BBTI in VA PCMH settings. Three approaches will be used to measure outcomes: (1) RE-AIM framework; (2) CFIR-guided qualitative interviews, with site PIs and PCMH clinicians, to identify barriers and facilitators related to implementation outcomes; and (3) surveys, completed by site PIs and PCMH clinicians, to identify utilization of specific implementation strategies. Four sites were invited to participate (Baltimore, Durham, Minneapolis, and Philadelphia) with Pittsburgh serving as the coordinating site, responsible for: (1) oversight of all study activities, (2) development and conduct of BBTI training, (3) providing support for the implementation strategies, and (4) directing data collection and analysis efforts.

As depicted in Figure 2, after study start-up procedures, the first step will involve training PCMH clinicians in BBTI at all sites. After BBTI training, site 1 (randomly selected) will have immediate access to, and support for, the bundle of implementation strategies for 12-months; this is the implementation phase of the trial. Sites 2, 3, and 4 will enter the pre-implementation monitoring phase for 6-, 12-, and 18-months, respectively, followed by their own 12-month implementation phase (random order). After each site has completed their 12-month implementation phase, access to the implementation strategies will be removed and each site will begin a 6-month post-implementation monitoring phase; however, for sites 1-3 we will continue to collect data to evaluate long-term sustainability through study month 39. Data collection will occur through all phases of the trial.

Figure 1. Study timeline.

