Maintenance will measure the sustainability of Reach, Effectiveness, Adoption, and Implementation during the 6-month post-implementation phase as well as during the long-term sustainability period (>6-months). The outcomes from the sustainability periods will then be compared to the outcomes during the pre- and implementation phases. The same operational definitions as described above will be used for Reach, Effectiveness, and Implementation. For Adoption, comparisons will be based on the rate a clinician delivers BBTI over time within each study phase. For example, the number months a PCMHI clinician Adopts BBTI (i.e., delivers BBTI to a Veteran) relative to the number of months [n=6] in the post-implementation phase.

Specific Aim 2: To identify specific strategies that help promote the implementation of BBTI in PCMHI using qualitative interviews and utilization surveys.

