| Same day/PC patients (%) | 5.69                                                       | 5.46   | 5.35   | 5.24   | 5.13   | 5.02   | 4.80     |
| Power (%)                | 100                                                        | 100    | 99.96  | 99.02  | 90.03  | 59.25  | --       |

Descriptive statistics will be used to characterize the participating sites, PCMHI clinicians who are trained in BBTI (enrolled and not enrolled), and Veterans who received insomnia-related care in Primary Care/PCMHI (e.g., BBTI, CBT-I). Key enrolled clinician variables (self-report) will include socio-demographics, training, and work experience (e.g., degree, prior insomnia experience, duration working in PCMHI). For Veterans, variables of interest, from CPRS/CDW, include socio-demographics, vitals, service connection, combat history, and medical and psychiatric disorders, prescription medications, healthcare utilization, and information from progress notes (e.g., ISI scores). For Reach, Adoption, Implementation, and Maintenance outcomes, generalized linear mixed models will be used to compare the impact of the implementation strategy bundle across the three study phases for each site. These models will include a fixed main effect for study phase (pre, implementation, post) and random effects for clinician (nesting of Veterans within clinicians) and site (nesting of Veterans and clinicians within site); the primary comparison will be pre-implementation vs. implementation, with the secondary comparison implementation vs. post-implementation and long-term sustainability. Also, a we will conduct a comparison of outcomes from the study phases vs. a historical period prior to the study (1/1/20 – 12/31/20). While we did not power the study to assess interactions, to the extent possible, a fixed effect for site and the interaction between site and phase, will be introduced to assess differences between sites at the same study phase and differences between sites for the primary and secondary comparisons (e.g., differences from pre-implementation to implementation and from implementation to post-implementation, site 2 vs. site 3).

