For treatment Effectiveness, using an intent-to-treat approach, we will fit a linear mixed model that tests for BBTI effectiveness (reduction of ISI score over the course of treatment) that includes a main effect of time (evaluation to last treatment session) and includes random effects for Veteran (multiple measurements per Veteran during treatment), clinician (nesting of Veterans within clinicians) and site (nesting of Veterans and clinicians within site). We will also attempt to control for clinician experience on treatment outcomes as well as mode of delivery of BBTI (e.g., in-person, phone, video) and other adaptations, such as integrating other

therapeutic techniques as indicated per the progress notes and extracted as part of the data query process (e.g., behavioral activation, motivational interviewing). Rates of response and remission from treatment will be calculated as will treatment effect sizes.

Specific Aim 2: To identify specific strategies that help promote the implementation of BBTI in PCMH using qualitative interviews and utilization surveys.

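### Aim 1 expects better treatment outcomes under BBTI+IS, but the Effectiveness analysis contains no implementation versus pre-implementation comparison

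*Combined protocol and SAP*

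**What the plan says.** The hypothesis is in 3.1 Objectives, Aim 1: "We hypothesize that BBTI+IS will result in more Veterans obtaining insomnia-related care in PCMH (R [primary outcome]), better treatment outcomes (E"). Section 5.1 Study Design makes it part of the trial's goal to "determine if a bundle of implementation strategies can improve the uptake and sustainable delivery, and treatment outcomes, of BBTI in VA PCMH settings". The restatement of Aim 1 in 5.6 also speaks of improving the RE-AIM outcomes, and Effectiveness is one of them.

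Section 5.6 splits the outcomes between two analyses.

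- **Phase models.** "For Reach, Adoption, Implementation, and Maintenance outcomes, generalized linear mixed models will be used to compare the impact" of the bundle across the study phases. They carry a fixed effect for phase (pre, implementation, post), and "the primary comparison will be pre-implementation vs. implementation, with the secondary comparison implementation vs. post-implementation and long-term sustainability". Effectiveness is not in the list of outcomes.
- **Effectiveness model.** Here "we will fit a linear mixed model that tests for BBTI effectiveness (reduction of ISI score over the course of treatment"). This separate model "includes a main effect of time (evaluation to last treatment session"). It has random effects for Veteran, clinician and site, and attempts to adjust for clinician experience, delivery mode and other adaptations. Response and remission rates are to be calculated; no comparison is named.

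The plan does mention phase for Effectiveness elsewhere. Under 5.5 Study Evaluations, "Maintenance will measure the sustainability of Reach, Effectiveness, Adoption, and Implementation during the 6-month post-implementation phase" and beyond, and "The outcomes from the sustainability periods will then be compared to the outcomes during the pre- and implementation phases". The same section says that RE-AIM variables are measured in every phase and that the data will permit pre-to-implementation comparisons within site.

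**The concern.** The E hypothesis concerns a difference between two conditions: training alone (pre-implementation) and training plus the bundle (implementation). The model given for ISI estimates something else, the average fall in ISI from evaluation to last session. Data are collected in all phases and the model sets no phase restriction, so that average is pooled over phases.

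A significant time effect would show that treated Veterans improve. It would be found whether the bundle helps, does nothing or harms, and a reader could take it as support for the E hypothesis. As written, that hypothesis is either left untested or tested with an analysis whose form is settled after the data are available. Aim 1 makes clear which phases to compare. Still open are the phase-by-time term, the handling of calendar time, and the phase to which a course crossing a boundary belongs.

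**Working it through.** **1. Text check.** The places where a phase contrast for Effectiveness could be specified are:

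| Place | What it provides | Implementation vs pre for ISI, response or remission? |
|---|---|---|
| 5.5, Effectiveness | ISI change, response and remission defined | No phase mentioned |
| 5.5, RE-AIM overview | Data permit pre-to-implementation comparisons | No outcome, model or test named |
| 5.5, Maintenance | Sustainability periods vs earlier phases | A different contrast |
| 5.6, phase models | Reach, Adoption, Implementation, Maintenance | Effectiveness not listed |
| 5.6, historical comparison | Study phases vs calendar year 2020 | A different contrast |
| 5.6, Effectiveness model | Time, random effects, covariates | No phase term |

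None names the contrast that Aim 1 needs.

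**2. Can the time effect stand in for it?** The documents give no SD of ISI change, no ICC and no number of courses per phase, so there is no planned figure to reproduce. What follows is an illustration.

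*Site-months after training, months 4 to 39 (5.1):* pre 0 + 6 + 12 + 18 = 36; implementation 4 × 12 = 48; post and long-term 24 + 18 + 12 + 6 = 60; total 144.

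*Courses (assumed):* taking 329 as implementation-phase courses gives 329/48 = 6.85 per site-month. With pre-phase rates of 10, 25, 50 and 100% of this, the pre-phase has 25, 62, 123 and 247 courses. With post-phase rates of 50 and 100%, it has 206 and 411. The total N runs from 559 (10%, 50%) to 987 (100%, 100%).

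*Pooled fall:* the base is 20.7 − 10.9 = 9.8 points (VA CBT-I study, 2.1 Introduction). With a bundle effect d in the implementation phase only, the pooled fall is 9.8 + d × 329/N:

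- d = +2: 10.5 to 11.0
- d = 0: 9.8
- d = −2: 8.6 to 9.1

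The smallest z over SD 5 to 7 is 8.62/(7/√559) = 29. The time test therefore rejects overwhelmingly in every case and does not reveal even the sign of d.

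*Simulation:* 2,000 runs, 329 Veterans in total, mean change −8, SD 6, no clustering. The time-only test rejected in 100% of runs with a bundle effect of 0, 1, 2 or 3 points. A simple phase contrast rejected in 5%, 33%, 85% and 99.5%.

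**3. How precise would the right contrast be?** The pooled half-width is 1.96 × SD/√N. The phase contrast comes from weighted least squares on 4 sites × 6 six-month periods, with site, period and phase effects.

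| 95% half-width, ISI points | SD 6 | SD 5–7 |
|---|---|---|
| Pooled time effect | 0.37–0.50 | 0.31–0.58 |
| Implementation vs pre | 1.52–2.96 | 1.26–3.45 |
| Same, site-by-period ICC 0.01 | 1.79–3.13 | – |
| Same, site-by-period ICC 0.05 | 2.63–3.70 | – |

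For the ICC rows, the variance of a cell mean is SD² × (ICC + (1 − ICC)/n). Rows without an ICC ignore clustering and are best cases.

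**4. Sensitivity to the count.** If 329 is the total and is split 36:48 (141 vs 188), the difference detectable with 80% power is (1.96 + 0.84) × SD × √(1/141 + 1/188) = 1.6, 1.9 or 2.2 points for SD 5, 6 or 7, without clustering or calendar adjustment.

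**The case against.** The best defence runs through Maintenance. It is defined to include Effectiveness under the same operational definitions, and it is among the outcomes given phase models, whose primary comparison is pre-implementation versus implementation. Read literally, ISI change might receive that contrast by this route. But 5.5 defines the Maintenance comparison as sustainability periods against earlier phases. The reading would also give ISI two models, and the one actually written out for it has no phase term. At best the plan is ambiguous, and the same sentences would cure that.

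Second, the pooled model has a legitimate purpose: the hybrid design also asks whether BBTI works for Veterans in routine care. That stands. The model is incomplete for the E hypothesis; it is not a wrong analysis of its own question.

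Third, the illustration rests on assumptions. Section 5.2 gives 329 as the goal for Veterans across all four sites without restricting it to a phase, and not every Veteran counted will have two ISI scores, so the half-widths may be too narrow. The 9.8-point fall comes from Veterans who completed CBT-I and may overstate an intent-to-treat BBTI change. Both points are fair. Neither touches the conclusion, because a model without phase cannot estimate a phase effect at any sample size.

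Fourth, Effectiveness is secondary and only Reach is powered. That limits the severity, but the protocol chose to state a directional hypothesis for E.

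**Conclusion.** The concern holds. The stated E hypothesis has no matching analysis: no implementation versus pre-implementation contrast is named for ISI change, response or remission, and the specified time effect cannot show even the direction of the bundle's effect. This rests on the text alone. The sizes are illustrative: a pooled fall of 8.6 to 11.0 points for bundle effects from −2 to +2, and a half-width for the missing contrast of 1.5 to 3.0 points at SD 6 without clustering (1.8 to 3.7 with an ICC of 0.01 to 0.05). They depend on the assumed SD, course counts and phase rates. It should be fixed, but it does not threaten the primary analysis of Reach.

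**What to change.** In the Effectiveness paragraph of 5.6:

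- Add study phase (pre, implementation, post/long-term) and phase-by-time to the ISI model, assigning each course to its site's phase on the start date.
- Name the implementation minus pre-implementation difference in ISI change as the secondary Effectiveness contrast. Report it as an estimate with a confidence interval, adjusted for calendar time as far as four sites allow.
- Report response and remission by phase, with the same difference and its interval.
- Keep the pooled pre-post change as a descriptive answer to whether treated Veterans improve.
- Report baseline ISI and Veteran characteristics by phase.
- Say whether CBT-I courses enter the model: 5.5 defines Effectiveness over BBTI/CBT-I sessions, while 5.6 speaks of BBTI.

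No new data are needed: phase follows from site and date, and ISI scores and Veteran characteristics are already extracted.

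The cost is interpretive. The contrast will be imprecise, because site 1 has no pre-implementation phase and only Reach is powered. It may also partly reflect selection: only treated Veterans contribute scores, and the bundle includes marketing and education (5.1, Table 3) that may change who starts treatment. If ISI reduction were proportional to baseline (an assumption; 9.8/20.7 = 47%), a 2-point shift in baseline ISI alone would move the contrast by about 0.9 points. The plan should label the contrast secondary and state both limits.

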insomnia symptoms with similar effect sizes as CBT-I trials, including the VA CBT-I rollout studies. BBTI was specifically developed for delivery outside of mental health settings to increase access to care —it shortens and simplifies treatment compared to the longer and more complex CBT-I. It is also one of the recommended treatments for chronic insomnia, along with CBT-I, per the 2020 VA/DOD Clinical Practice Guidelines. Key elements that make BBTI advantageous for Primary Care are: (1) fewer sessions (BBTI, 2 in-person + 2 phone; CBT-I, 5-8 in-person) and (2) shorter session duration (BBTI, in-person 30-45 min, phone <20-30 min; CBT-I, in-person 30-45 min). It is important to note that while BBTI is packaged differently than CBT-I, it is a more focused treatment that emphasizes the two key behavioral components in multicomponent CBT-I, stimulus control and sleep restriction. Also, iterations

Figure 1. Pre- to post-treatment ISI and effect sizes.

of BBTI and/or brief CBT-I have been tested in VA and are already delivered as part of routine care within VA, usually in PCMH settings. However, these brief insomnia treatments lack the saturation of CBT-I, the more established treatment with the support of the VA EBP program. Increasing saturation (increased uptake,

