### **5.3 Informed Consent Procedures**

VA employee participants—site PIs and PCMH clinician—will be invited to participate in this trial (see section 5.4). Those who volunteer to participate will complete a verbal informed consent by phone, administered by study staff at the hub site in Pittsburgh. See Appendix 10.2 for the study information sheet that will be provided to all potential participants prior to consent. We are requesting a waiver of documentation of informed consent to conduct the consent process by phone. VA employee participants will be informed that audio-recorded interviews are involved and consent for audio-recording will be documented along with their consent to participate in the study. During the interviews, immediately after recording begins, study staff will ask all participants if they agree to being recorded. If not agreeable with recording, the recording will stop, but the interview will still proceed. This agreement/disagreement will be documented by study staff and stored in the study network drive where audio-recordings are stored. Other than their name, no other PHI will be collected from VA employee participants.

We will collect retrospective data, from the electronic medical records, for Veterans who receive BBTI from PCMH clinician at the participating sites. No information will be collected directly from Veterans; a waiver of informed consent and a waiver of HIPAA will be requested. Veterans will be receiving usual care (BBTI), thus, the risk to Veterans is minimal and limited to breach of confidentiality from the retrospectively collected data.

Study staff at the hub site and participating sites will complete and stay up to date on the required trainings for the conduct of human subjects research.

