### **5.4 Inclusion/Exclusion Criteria**

Site PIs and PCMH clinician are the focus of this study with retrospective data collection for Veterans who receive BBTI (or CBT-I) delivered by PCMH clinician at the participating sites. Each participating site PI will be invited to participate in this study. PCMH clinician at each participating site will be invited, by their site PI, to attend a training for BBTI. Those who attend and complete BBTI training will be invited to participate in this study. PCMH clinician who have been previously training in CBT-I will not be required to take the BBTI training as BBTI is adapted from CBT-I and there is significant overlap. Women and minorities will be included in this study.

There will be retrospective data collection from electronic health records and databases for Veterans who receive care in PCMH and engage in BBTI (or CBT-I) from a PCMH clinician.

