|                    |            |                                                                                                                  |
|--------------------|------------|------------------------------------------------------------------------------------------------------------------|
| Diagnoses          | ICD-10:    | F51.0, F51.01, F51.02, F51.03, F51.04, F51.05, F51.09, G47.00, G47.01, G47.09                                    |
|                    | ICD-9:     | 307.41, 307.42, 780.50, 780.51, 780.52                                                                           |
| Sedative-hypnotics | On label:  | diphenhydramine, doxepin, eszopiclone, prazosin, ramelteon, suvorexant, temazepam, triazolam, zaleplon, zolpidem |
|                    | Off label: | hydroxyzine, melatonin, trazodone, others specifically indicated for sleep                                       |

Effectiveness will be measured as the change on the ISI from the initial score obtained (e.g., PCMH initial evaluation, BBTI/CBT-I session 1) to the last BBTI/CBT-I session. The ISI is commonly used within the VA and is easily accessible within VA electronic health records through the Mental Health Assistant toolbox as well as Behavioral Health Lab software, which was developed for use in PCMH. ISI data may also be extracted from CPRS progress notes (e.g., BBTI progress notes). The ISI has well-established psychometrics with good reliability and validity. It is standard practice as part of insomnia-related treatment (i.e., BBTI and CBT-I) and PCMH treatment (e.g., depression, anxiety, pain) to use measurement-based care (e.g., ISI, PHQ-9) and include outcome measures in progress notes to inform care and track treatment progress. For Effectiveness to be calculated, ISI scores from each BBTI/CBT-I session (e.g., entered in a BBTI progress note or CBT-I templated note) by PCMH clinicians will be extracted through the automated CDW queries to calculate outcomes for each Veteran. Rates of treatment response and remission will also be calculated. Response is a reduction of ≥8 points on the ISI from pre- to post-treatment. Remission is achieving a post-treatment response and an ISI <8. Previous BBTI trials found treatment response rates of 42-77% and remission rates of 28-53%.

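### Effectiveness is defined over BBTI and CBT-I sessions together, but the ISI model is labelled a test of BBTI effectiveness, with no stated analysis set and no treatment-type term

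*Combined protocol and SAP*

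**What the plan says.** **Outcome definition (5.5, Effectiveness).** ISI change is measured "from the initial score obtained (e.g., PCMH initial evaluation, BBTI/CBT-I session 1) to the last BBTI/CBT-I session". The data source covers both treatments: "ISI scores from each BBTI/CBT-I session (e.g., entered in a BBTI progress note or CBT-I templated note) by PCMH clinicians will be extracted". Response and remission rates follow, and are set beside earlier BBTI trials (response 42-77%, remission 28-53%).

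**Whose data are used.** Section 5.4 collects records on "Veterans who receive care in PCMH and engage in BBTI (or CBT-I) from a PCMH clinician", and 5.2 also mentions delivery of either treatment. Section 5.3 is narrower: data are collected "for Veterans who receive BBTI from PCMH clinician at the participating sites".

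**Model (5.6, Effectiveness).** The plan is: "we will fit a linear mixed model that tests for BBTI effectiveness (reduction of ISI score over the course of treatment". The listed terms are a main effect of time, random effects for Veteran, clinician and site, and attempted control for clinician experience, mode of BBTI delivery and other adaptations. No analysis set is stated. No term, stratum or subset separates BBTI from CBT-I.

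**Why CBT-I cases can arise.** Section 5.4 says "PCMH clinician who have been previously training in CBT-I will not be required to take the BBTI training". Table 2 (5.1) makes the choice between BBTI and CBT-I a shared decision. Section 2.1 describes the length difference as "fewer sessions (BBTI, 2 in-person + 2 phone; CBT-I, 5-8 in-person".

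**Later use.** In 5.5, Maintenance carries the same definition of Effectiveness into the comparison of the sustainability periods with the pre-implementation and implementation phases.

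**The concern.** The outcome definition and the stated question do not match. One section defines the measurement over two treatments. The next declares the result a test of one of them.

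Three things are at stake:

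- **The estimate.** The clinical summary of the trial (ISI change, response, remission, effect size) could rest partly on a different and longer treatment, and then be compared with benchmarks from BBTI trials.
- **The time effect.** The last treatment session falls after four sessions for one treatment and after five to eight for the other, so a single time effect mixes treatment type with treatment length. Since 2.1 describes CBT-I as in-person and BBTI as half by phone, the delivery-mode covariate would also partly stand in for treatment.
- **The phase comparison.** The implementation bundle promotes BBTI, so the BBTI/CBT-I mix may differ between phases. In the Maintenance comparison, a change in mix could look like a change in effectiveness.

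**Working it through.** The plan gives no sample size, power or effect size for the Effectiveness model, so there is no figure to reproduce. The check has two parts.

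**1. Reading the sections together**

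- If 5.5 governs, the model population includes CBT-I recipients, and the BBTI label in 5.6 does not describe what is estimated.
- If the BBTI wording in 5.6 and the population in 5.3 govern, the model is BBTI-only. That contradicts the outcome definition in 5.5 and the population in 5.4.
- Under either reading the sections need reconciling.

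**2. How far pooling could move the result**

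Inputs from the documents:

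- CBT-I response of 60% and mean ISI from 20.7 to 10.9, a fall of 20.7 − 10.9 = 9.8 points (2.1, a VA study; the response rate is for treatment completers).
- BBTI response of 42-77% (5.5, earlier trials).

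The CBT-I share *s* is not given and is assumed, from 10% to 75%.

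Pooled response = (1 − s) × BBTI response + s × 60%.

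| Assumed CBT-I share | True BBTI 42% | True BBTI 60% | True BBTI 77% |
|---|---|---|---|
| 10% | 43.8% | 60% | 75.3% |
| 25% | 46.5% | 60% | 72.75% |
| 50% | 51.0% | 60% | 68.5% |
| 75% | 55.5% | 60% | 64.25% |

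For example, at 50%: 0.5 × 42 + 0.5 × 60 = 51.0, and 0.5 × 77 + 0.5 × 60 = 68.5.

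The shift in mean ISI fall is s × (9.8 − B), where B is the BBTI fall. The text gives no value for B (Figure 1 was not available for this check), so B is assumed. At s = 50%:

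- B = 6 gives 0.5 × 3.8 = +1.9 points
- B = 8 gives 0.5 × 1.8 = +0.9 points
- B = 9.8 gives 0
- B = 12 gives 0.5 × (−2.2) = −1.1 points

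**Change of mix between phases.** Suppose neither treatment changes, but the CBT-I share falls from 50% to 10%. With BBTI response at 42%, the pooled rate goes from 51.0% to 43.8%, an apparent loss of 7.2 points. With BBTI response at 77%, it goes from 68.5% to 75.3%, an apparent gain of 6.8 points.

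**The case against.** **Pooling is not stated outright.** A reader might infer that 5.6 specifies a pooled model. It does not: it names no analysis set, and its BBTI wording together with 5.3 allows a BBTI-only reading. This stands as a limit on the claim. It does not remove the problem, because that reading conflicts with 5.5.

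**Including CBT-I is deliberate.** The audit-and-feedback row of Table 3 queries RE-AIM outcomes for Veterans given either treatment, so as to describe all insomnia treatment in PCMHI, and 5.5 calls CBT-I engagement relevant. It would be wrong to say that nothing justifies collecting CBT-I data. Only the BBTI label on a pooled result is open to challenge.

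**Overstatement of BBTI is not shown.** A reader might infer that pooling inflates the BBTI result because the cited CBT-I fall is large. The documents support no direction. The 60% CBT-I response lies inside the 42-77% BBTI range, and it comes from completers whereas 5.6 specifies an intent-to-treat approach. Section 2.1 reports similar effect sizes and no significant difference in a direct comparison delivered by PCMHI clinicians. The best expectation from the documents is a shift near zero.

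**Clustering of CBT-I by clinician or site is also an inference.** Section 5.4 excuses CBT-I-trained clinicians from BBTI training but does not say they will deliver CBT-I. Random effects for clinician and site, and adjustment for experience, would absorb part of any clustering.

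**Attribution fails for another reason.** A reader might infer that separating the treatments would let the ISI change be attributed to BBTI. It would not. The model is an uncontrolled pre-post comparison, so regression to the mean and natural course remain even among BBTI recipients alone.

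**Effectiveness is not the primary outcome.** Reach is. This stands, and it limits the weight of the point.

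**Conclusion.** The point holds as a mismatch between the outcome definition and the declared question. Following 5.5 as written gives a mixed-treatment estimate presented as BBTI effectiveness, and the planned model has no term that could show whether the two treatments differ.

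In the illustration, a 50% CBT-I share moves the response rate by +9 points (42% to 51%) or −8.5 points (77% to 68.5%), and by nothing if the treatments perform equally. These figures rest on an assumed share and on response rates from different studies. They show what is possible and do not forecast a bias.

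The 5.6 Effectiveness model has no phase term, so a shift in mix matters through the Maintenance comparison rather than through that model. The primary Reach analysis is not affected. This is a cheap improvement rather than a defect that threatens the trial.

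**What to change.** 1. In 5.6, make Veterans who initiated BBTI the analysis set for the BBTI Effectiveness model, response, remission and effect sizes. Classify each Veteran by the first treatment note, and keep that classification if the Veteran later switches.
2. Report the pooled BBTI/CBT-I set as a secondary analysis, with treatment type and treatment-by-time as fixed effects. Read it descriptively, because treatment is chosen and not randomised.
3. Apply the same BBTI analysis set when Effectiveness is compared across phases under Maintenance.
4. Align 5.3, 5.4 and 5.5 on whose data are collected and which of them enter each estimate.

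**Cost.** The change is to wording, plus a simple classification rule. Section 5.5 already draws on separate BBTI and CBT-I notes, so new data collection does not appear necessary. ISI scores taken from other software would have to be linked to the Veteran's first treatment note. The sample for the BBTI estimate will be somewhat smaller. The change makes the estimate describe the treatment it names; the comparison remains uncontrolled.
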